## **Analyses**

The summary statistics (including number, mean, median, Q1, Q3, standard deviation, minimum and maximum) of all laboratory variables (central laboratory values and changes from baseline) will be calculated for each visit or study assessment (baseline and each post-baseline time point) by treatment group. For eosinophils and liver function tests (AST, ALT, alkaline phosphatase, and total bilirubin), mean changes from baseline with the corresponding SEM will be plotted over time in each treatment group. This section will be organized by biological function as specified above.

The incidence of PCSAs (list provided in [Appendix F](#)) at any time during the TEAE period will be summarized by biological function and by treatment group whatever the baseline level and/or according to the following baseline status categories:

- Normal/missing.
- Abnormal according to PCSA criterion or criteria.

For parameters for which no PCSA criteria are defined, similar table(s) using the normal range will be provided.

For PCSA analyses, the laboratory measurements obtained at either scheduled or unscheduled visits should be used; and, both the centralized and local test results should be used, as long as their available dates/time is different from each other's. Centralized data will be used preferentially to the local measures in the PCSA analyses when measurements are performed on the same date and at the same time for a given laboratory test.

A listing of PCSAs will be provided.

### ***Drug-induced liver injury***

If there is any imbalance in the incidence of liver-related adverse events across the treatment groups, analysis of liver-related adverse events will be performed.

The liver function tests (LFT), namely AST, ALT, alkaline phosphatase, and total bilirubin, are used to assess possible drug-induced liver toxicity. The proportion of patients with PCSA values at any post-baseline visit by baseline status will be displayed by treatment group for each parameter. The proportion of patients with PCSA values at any post baseline visit may be displayed by duration of exposure for each treatment group.

Listing of possible Hy's law cases identified by treatment group (eg, patients with any elevated ALT > 3 x ULN, and associated with an increase in bilirubin  $\geq 2$  x ULN) with ALT, AST, alkaline phosphatase, total bilirubin, and the following complementary parameters: conjugated bilirubin and creatine phosphokinase, serum creatinine, complete blood count, HCV RNA.

The normalization by parameter (to  $\leq 1$  x ULN or return to baseline) of elevated liver function tests will be summarized by categories of elevation (> 3 x, 5 x, 10 x, 20 x ULN for ALT and AST, > 1.5 x ULN for alkaline phosphatase, and > 1.5 x and 2 x ULN for total bilirubin), with the following categories of normalization: never normalized, normalized despite treatment continuation of IMP, or normalized after IMP discontinuation. Note that a patient will be counted only under the maximum elevation category.

### ***Change in Blood Eosinophil***

Mean ( $\pm$  SEM) and median (with the interquartile range) changes from baseline in eosinophil with the corresponding standard error will be plotted over time in each treatment group for patients with baseline blood eosinophil < 0.5 Giga/L and patients with baseline blood eosinophil  $\geq 0.5$  Giga/L.

Number (%) of patients with post-baseline peak blood eosinophil  $\geq 1$  Giga/L,  $\geq 3$  Giga/L and  $\geq 5$  Giga/L will also be summarized in each treatment group and by baseline blood eosinophil status (All, < 0.5 Giga/L,  $\geq 0.5$  Giga/L). A similar table will be produced using the following thresholds  $\geq 0.5$  Giga/L,  $\geq 1$  Giga/L,  $\geq 3$  Giga/L and  $\geq 5$  Giga/L for baseline and post-baseline assessments.

A summary of number (%) of patients with maximum change from baseline in blood eosinophil  $\leq 0.5$  Giga/L, > 0.5 -  $\leq 1$  Giga/L or > 1 Giga/L will also be provided by treatment group and by baseline blood eosinophil level ( $\leq 0.5$  Giga/L, > 0.5 -  $\leq 1$  Giga/L, > 1 Giga/L).

### **2.8.3 Vital signs**

Vital signs include the systolic and diastolic blood pressure (mmHg), heart rate (beats per minute), respiratory rate (breaths per minute) and body temperature (degree Celsius), and will be assessed at all scheduled visits except Week 18. Body weight (kg) will be measured at the first screening visit, Day 1, Week 12/EOT and EOS.

The summary statistics (including number, mean, SD, median, Q1, Q3, minimum and maximum) of all vital signs variables (raw data and changes from baseline) will be calculated for each visit or study assessment (baseline and each post-baseline time point) by treatment group. For all parameters, mean changes from baseline with the corresponding standard error will be plotted over time (at the same time points) in each treatment group.

The incidence of PCSAs at any time during the TEAE period will be summarized by treatment group irrespective of the baseline level and/or according to the following baseline status categories:

- Normal/missing.

- Abnormal according to PCSA criterion or criteria.

A listing of PCSAs will be provided.

#### **2.8.4 Oxygen saturation**

Oxygen saturation (%) will be measured by pulse oximetry before the bronchoscopy procedure (ie, at the second visit of screening and Week 12/EOT) to ensure patient suitability.

The summary statistics (including number, mean, SD, median, Q1, Q3, minimum and maximum) for raw data and changes from baseline will be calculated for each visit by treatment group.

#### **2.8.5 Electrocardiogram**

##### **Quantitative parameters**

A single standard 12-lead ECG will be performed at Screening, Day 1 and Week 12/EOT, and centrally read by an ECG core lab. The following parameters will be received from the ECG core lab and will be analyzed: RR interval (msec), HR (beats/min), PR interval (msec), QRS interval (msec), QT interval (msec), heart-rate corrected QT interval (msec) using Bazett's (QTcB) and Fridericia's formula (QTcF), and QRS axis (degrees).

The summary statistics (including number, mean, SD, median, Q1, Q3, minimum and maximum) of all quantitative ECG variables (raw data and absolute changes from baseline), except RR interval, will be calculated for each visit or study assessment (baseline, each post-baseline time point) by treatment group.

The incidence of PCSAs at any time during the TEAE period will be summarized by treatment group irrespective of the baseline and/or according to the following baseline status categories:

- Normal/missing.
- Abnormal according to PCSA criterion or criteria.

A listing of PCSAs will be provided. A separate listing of patients with QTcB/QTcF >480 ms and/or change from baseline in QTcB/QTcF >60 ms will also be provided, using all post-dose timepoints.

##### **Qualitative ECG findings**

The incidence of qualitative findings by the ECG core lab will be summarized by treatment group, separately for ECGs done prior the first dosing and for ECGs done after, for all assessments done during the TEAE period. These findings will include:

- The overall ECG conclusion (Normal ECG; Abnormal ECG, clinically insignificant; Abnormal ECG, potentially clinically significant; ECG unable to evaluate; ECG unable to evaluate but measurements provided are correct).

- All findings sorted by category of finding (rhythm, supraventricular arrhythmias, ventricular arrhythmias, AV conduction, intraventricular conduction, axis and voltage, chamber hypertrophy and enlargement, ST-T abnormalities, ischemia and infarction, technical statements) and finding (refer to the ECG manual for further details about the findings).

## 2.9 ANALYSIS OF PHARMACOKINETIC DATA

All endpoints in this section are considered as additional endpoints in the study.

### 2.9.1 Dupilumab concentration analysis in serum

Concentrations of dupilumab in serum will be measured at Day 1 predose, Week 2, Week 6, Week 8, Week 12/EOT, and for patients who do not enter the OLE, at Week 18 and EOS.

Concentration will be summarized in the PK population using arithmetic and geometric means, SD, SEM, coefficient of variation (CV), minimum, median and maximum per sampling time. Values will be expressed in the tables with no more than three significant figures. Mean concentrations with the corresponding standard error will be plotted over time.

See data handling conventions for PK variables in [Section 2.11.4](#).

### 2.9.2 Anti-drug antibodies analysis

#### ADA status

Anti-dupilumab antibody status (negative or titer value, if positive in the ADA assay) will be assessed at Day 1, Week 12/EOT, and, for patients who do not enter the OLE, at EOS.

Status in the ADA assay will be classified as the following:

1. Pre-existing immunoreactivity is defined as:

An ADA positive response in the assay at baseline with all post treatment ADA results negative

OR

An ADA positive response at baseline with all post treatment ADA responses less than 4-fold over baseline titer levels.

2. Treatment-emergent response is defined as an ADA positive response in the assay post first dose, when baseline results are negative or missing.
3. Treatment-boosted response is defined as an ADA positive response in the assay post first dose that is greater-than or equal to 4-fold over baseline titer levels, when baseline results are positive.

### **Titer values (titer value category)**

- Low (Titer < 1000).
- Moderate ( $1000 \leq \text{Titer} \leq 10000$ ).
- High (Titer > 10000).

ADA positive samples will be further characterized for presence of neutralizing antibody (NAb) response in the NAb assay.

### **ADA status summary**

The following summary will be provided based on the ADA population:

- Number (%) of patients with pre-existing immunoreactivity.
- Number (%) of patients with treatment-emergent ADA.
- The summary statistics (including number, median, Q1, Q3, minimum and maximum) of the peak post-baseline titer for patients with treatment-emergent ADA.
- Number (%) of patients with treatment-boosted ADA.
- For patients with treatment-boosted ADA:
  - The summary statistics (including number, median, Q1, Q3, minimum and maximum) of the peak post-baseline titer.
  - The summary statistics (including number, mean, SD, median, Q1, Q3, minimum and maximum) of the ratio of peak post-baseline titer to baseline titer.
- Number (%) of patients with NAb status
- Listing of ADA peak titer levels and NAb status

### **Kinetics of treatment-emergent ADA response**

Number (%) of patients with treatment-emergent ADA response at each visit will be summarized by each treatment group.

Plot of percentage of patients with treatment-emergent ADA response at each visit will be provided by each treatment group.

### **Association of ADA with PD endpoints**

Associations between ADA variables and main PD endpoints may be explored if needed.

## 2.10 EXPLORATORY PHARMACOKINETIC/PHARMACODYNAMIC ANALYSIS

The PK/PD analysis will be done on the PK/PD population as defined in [Section 2.2.5](#). The relationship between dupilumab concentration and selected bronchoscopy biomarkers will be explored through scatter plots. A statistical modeling will be performed if relevant.

## 2.11 DATA HANDLING CONVENTIONS

### 2.11.1 General conventions

The following formulas will be used for computation of parameters.

#### *Demographic formulas*

Age is calculated as:

$$\text{Integer part of (informed consent date – birth date)/365.25}$$

Age of onset of asthma is calculated as:

$$\text{Integer part of (asthma onset date – birth date)/365.25}$$

Due to the Germany regulation, German patients provide the January 1st of birth year, instead of standard date birth. The first date of the birth quarter will be used as birth date approximately.

Time since first diagnosis of asthma (years) is calculated as:

$$\begin{aligned} & (\text{Year of randomization – Year of first diagnosis of asthma}) + \\ & (\text{Month of randomization – month of first diagnosis of asthma})/12 \end{aligned}$$

Time since cessation of smoking (month) is calculated as:

$$(\text{Year of randomization – Year of cessation}) \times 12 + (\text{month of randomization – month of cessation})$$

Time since last asthma exacerbation (months) is calculated as:

$$\begin{aligned} & (\text{Year of randomization – Year of last asthma exacerbation}) \times 12 + \\ & (\text{Month of randomization – Month of last asthma exacerbation}) \end{aligned}$$

BMI is calculated as:  $\text{Weight in kg/ (height in meters)}^2$

Smoking quantity (pack-year) is calculated as following:

$$\text{Number of pack-year} = (\text{packs smoked per day}) \times (\text{years as a smoker}) \times 365.25$$

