### ***Disease characteristics***

The following baseline disease characteristics will be summarized by treatment group and overall:

- ICS dose level (medium, high as defined in [Appendix B](#)).
- Age of asthma onset (quantitative and in classes: <18 years, ≥18-<40, ≥40 years).
- Time since first diagnosis of asthma (years).
- Time since last severe asthma exacerbation (months); a severe asthma exacerbation prior to the study is defined as any treatment with 1 systemic (oral or parenteral) steroid burst or more for worsening asthma or hospitalization or an emergency/urgent medical care visit for worsening asthma.
- Number of severe asthma exacerbation experienced within 1 year before Visit 1 (quantitative variable and qualitative variables: 0, 1, 2, 3, ≥4).
- Number of severe asthma exacerbations requiring hospitalization or urgent medical care experienced within 1 year before Visit 1 (quantitative variable and qualitative variables: 0, 1, 2, 3, ≥4).
- Smoking history (Never, Former), time since cessation of smoking (years) and smoking quantity in pack-years for former smokers.
- Baseline spirometry data including pre-bronchodilator Forced Expiratory Volume in One Second (FEV1, in L, quantitative and in class: ≤1.75 and >1.75L), percent predicted FEV1 (%), quantitative and in class: <60% and ≥60%), post bronchodilator FEV1 (L) and FEV1 reversibility (%).
- AM and PM Peak Expiratory Flow (PEF) (L/min).
- AM and PM symptom scores.
- Asthma control questionnaire 5-question version (ACQ-5) score (quantitative and in classes : ≤2 and >2).
- Number of inhalations/day of salbutamol/albuterol or levosalbutamol/levalbuterol for symptom relief in a 24-hr period.
- Hypersensitivity to aspirin or nonsteroidal anti-inflammatory drug (NSAID; Yes, Ongoing condition).
- Blood eosinophils (quantitative and in class: <0.15 and ≥0.15 Giga/L; <0.3 and ≥0.3 Giga/L).
- FeNO in ppb (quantitative and in class: <50 and ≥50 ppb).
- Total IgE in IU/mL.

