**Table 4 - Conversation table for reliever medication: Levosalbutamol/Levalbuterol Nebulizer Solution**

Levosalbutamol/Levalbuterol Nebulizer Solution -Total Daily Dose (mg)	Number of puffs*
1.25	4
2.5	8
3.75	12
5	16

\*Conversion factor: levosalbutamol/levalbuterol nebulizer solution (1.25 mg) corresponds to 4 puffs

Example of levosalbutamol/levalbuterol Nebulizer-to-Puff Conversion: Patient received 3 levosalbutamol/levalbuterol nebulizer treatments (1.25 mg/treatment) between 7 and 11 AM. Total daily = 3.75 mg, i.e., 12 puffs.

Descriptive statistics on the number of puffs of reliever medications by 24 hours will be provided by treatment group and visit.

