**Table 7 - Periodical average of daily efficacy assessment**

Time point	Morning PEF, asthma symptom score	Evening PEF, asthma symptom score	Number of inhalations/day of salbutamol/albuterol or levosalbutamol/levalbuterol for symptom relief
Day 15	2-15	1-14	Diary day 1-14
Day 29	16-29	15-28	Diary day 15-28
Day 43	30-43	29-42	Diary day 29-42
Day 57	44-57	43-56	Diary day 43-56
Day 71	58-71	57-70	Diary day 57-70
Day 85	72-85	71-84	Diary day 71-84
Day 99	86-99	85-98	Diary day 85-98
Day 113	100-113	99-112	Diary day 85-112
Day 127	114-127	113-126	Diary day 113-126

Time point	Morning PEF, asthma symptom score	Evening PEF, asthma symptom score	Number of inhalations/day of salbutamol/albuterol or levosalbutamol/levalbuterol for symptom relief
Day 141	128-141	127-140	Diary day 127-140
Day 169	142-169	141-168	Diary day 141-168
Day 183	170-183	169-182	Diary day 169-182
Day 197	184-197	183-196	Diary day 183-196

Note: A diary day is defined as the period beginning with an Evening diary, and ending with the following day's Morning Diary. For example, diary day 14 includes the evening diary on day 14 and the morning diary on day 15.

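### Two derivation rules in SAP Section 2.11 give wrong values: pack-years are multiplied by 365.25, and the Day 113 reliever-use window contains the whole Day 99 window

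*SAP*

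**What the plan says.** **Pack-years.** Among the demographic formulas in Section 2.11.1, the SAP introduces the derivation with "Smoking quantity (pack-year) is calculated as following". The formula is packs per day, multiplied by years smoked, multiplied by 365.25; it ends "years as a smoker}) \times 365.25". The result goes into the baseline disease characteristics of Section 2.3.1, which list "smoking quantity in pack-years for former smokers".

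**Reliever-use windows.** Section 2.11.3 makes Table 7 the definition of the averaging periods for the daily diary variables. In the reliever column, Day 99 is "Diary day 85-98", Day 113 is "Diary day 85-112" and Day 127 is "Diary day 113-126". In the Day 113 row the morning PEF window is days 100-113 and the evening PEF window is days 99-112. The note under the table fixes how diary days map to calendar days: "diary day 14 includes the evening diary on day 14 and the morning diary on day 15". For the use of these data, Section 2.5.2 states: "Descriptive statistics on the number of puffs of reliever medications by 24 hours will be provided by treatment group and visit".

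Nothing else in the SAP rescales the smoking figure or explains the longer Day 113 window.

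**The concern.** Section 2.11 is operative text: it tells the programmer how each variable is computed.

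The smoking formula has a unit error. Its output carries the label of one quantity (pack-years) and the value of another (total packs). Followed literally, the baseline table for former smokers would show exposures that no person could have.

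The Day 113 reliever window breaks the pattern of its own table. It re-uses the previous time point's data, so Day 99 and Day 113 are not separate summaries, and reliever use at Day 113 covers a different period from PEF in the same row. A programmer who notices either slip and corrects it silently departs from the pre-specified derivation without a record.

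**Working it through.** **1. Pack-years**

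Inputs: the Section 2.11.1 formula, and the unit declared there and in Section 2.3.1.

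Unit check: (packs/day) × (years) = pack-years. Multiplying by 365.25 days/year gives (packs/day) × (days) = packs.

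| Packs/day | Years | SAP formula | Without the factor |
|---|---|---|---|
| 1 | 1 | 1 × 1 × 365.25 = 365.25 | 1 |
| 0.5 | 10 | 0.5 × 10 × 365.25 = 1,826.25 | 5 |
| 1 | 10 | 1 × 10 × 365.25 = 3,652.5 | 10 |

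The smoking histories are illustrations, not figures from the SAP. The ratio is 365.25 whatever history is used. In the age formulas of the same section, 365.25 is correctly a divisor that turns days into years. Here the duration is already in years, so neither multiplying nor dividing by it is needed.

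**2. Day 113 reliever window**

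Inputs: the Table 7 rows and the diary-day note.

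| Row | Evening PEF | Reliever (diary days) | Reliever length | Overlap with previous row |
|---|---|---|---|---|
| Day 99 | 85-98 | 85-98 | 98 − 85 + 1 = 14 | 0 |
| Day 113 | 99-112 | 85-112 | 112 − 85 + 1 = 28 | 98 − 85 + 1 = 14 |
| Day 127 | 113-126 | 113-126 | 126 − 113 + 1 = 14 | 0 |

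The same check on all 13 rows shows that the reliever window equals the evening PEF window in 12 of them; Day 113 is the exception. It is also the only row that overlaps the one before it. The Day 169 row is 28 days long too, but in all three columns and without overlap, so it is not a precedent.

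The intended window can be recovered in two ways:

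- Day 99 ends at diary day 98 and Day 127 begins at 113, so the gap to be filled is 99-112, which is 14 days.
- A diary day runs from one evening to the next morning. Diary days 99-112 therefore cover evenings 99-112 and mornings 100-113, exactly the two PEF windows in that row.

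Effect: let A be mean daily use over diary days 85-98 and B the mean over 99-112. With complete diaries the SAP's Day 113 value is (14A + 14B)/28 = (A + B)/2. The reported change from Day 99 is (A + B)/2 − A = (B − A)/2, half the true change. For illustration, with A = 6 and B = 2 puffs per day, the SAP reports (14 × 6 + 14 × 2)/28 = 4 instead of 2.

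**The case against.** The best argument on the other side is that neither slip can alter a treatment comparison, and that argument largely stands.

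- Smoking quantity is a summarised baseline characteristic. It is not a covariate in the main pharmacodynamic model, the FeNO model or the efficacy model. If it enters the Spearman correlations of Section 2.6.2.5, multiplying every value by the same positive constant leaves the coefficient unchanged.
- For the daily diary, the listed exploratory endpoints are morning and evening PEF at Weeks 2, 4, 6, 8 and 12. The analysis stated for reliever use after baseline is descriptive. Day 113 is Week 16 (16 × 7 + 1 = 113), and the reliever windows from Day 15 to Day 99 are sound.
- A value such as 1,826 pack-years would probably be caught at table review. With complete diaries the true Day 113 mean can be recovered as twice the reported Day 113 value minus the Day 99 value. The change is halved, not concealed.

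This limits the weight of the point but not its correctness. The chance that someone notices an error downstream is no reason to leave it in the plan. Nor is Week 16 only late follow-up: Section 1.4 allows the Week 12 bronchoscopy to move to Week 14 or 16, with up to two further doses. For a patient postponed to Week 16, diary days 99-112 are the fortnight just before the end-of-treatment visit, which is the fortnight the faulty window dilutes.

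**Conclusion.** Both errors hold as stated. The pack-year formula overstates every value by exactly 365.25, whatever the data. The Day 113 reliever average draws 14 of its 28 days (50%) from the Day 99 window, so a change between the two fortnights appears at half its size. The one-half figure assumes complete diaries; with gaps, the share depends on how many days are recorded in each fortnight.

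The consequences are confined to descriptive output: the smoking row of the baseline table and one reliever time point. Both look like typographical slips. They should still be corrected, because as written they are the pre-specified rules and they give wrong numbers.

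**What to change.** In Section 2.11.1, delete the multiplication by 365.25, so that pack-years equal packs per day times years as a smoker. In Table 7 of Section 2.11.3, change the Day 113 reliever entry to diary days 99-112. That window has 14 days, does not overlap Day 99 and matches the evening PEF window in the row.

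The cost is two text corrections to the SAP. No new data, design change or clinical decision is involved. Any derivation programs already written to the current text should be checked against the corrected rules.

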#### *Renal function formulas*

For patients  $\geq 18$  years old, creatinine clearance (CLcr) value will be derived using the equation of Cockcroft and Gault:

$$\text{CLcr (ml/min)} = (140 - \text{age}) \times \text{weight (kg)} \times (1 - 0.15 \times \text{sex (0-M, 1-F)}) / (0.814 \times \text{creatinine } (\mu\text{mol/l}))$$

CLcr will be calculated using the last weight measurement on or before the visit of the creatinine measurement and age at the lab sampling date. Here age is calculated as following:

$$\text{Age} = \text{integer part of } (\text{lab sampling date} - \text{birth date})/365.25$$

